8.3.7. Analysis of Safety Endpoint

Treatment-emergent adverse events (TEAEs) will be summarized by treatment arm. For each coded medical term, the proportion of subjects who experience at least one treatment-emergent:

- adverse event(s);
- adverse event(s) related to treatment;
- serious adverse event(s);
- serious adverse event(s) related to treatment;
- adverse event(s) leading to treatment/study discontinuation; or
- serious adverse event(s) leading to treatment/study discontinuation

will be reported. Subject incidence of TEAEs by severity (mild, moderate, severe) will also be presented. Events will be reported by MedDRA system organ class and preferred term. A listing of death(s), subjects who died of any cause during study, will be presented.

8.4. Additional Statistical Details

8.4.1. Hypothesis

This study will assess whether closed incision negative pressure therapy (ciNPT) reduces the surgical site complications (SSCs) compared to standard of care (SOC) among subjects who undergo a total knee arthroplasty (TKA) revision. The primary endpoint is measured by the proportion of subjects with SSC within 90 days of TKA revision among subjects in the mITT Analysis Set; the corresponding null and alternative hypotheses are:

Null: $\Delta_{\text{ciNPT-SOC}} = 0$

Alternative: $\Delta_{\text{ciNPT-SOC}} \neq 0$

where $\Delta_{\text{ciNPT-SOC}}$ is the difference in the proportion of subjects in the ciNPT group population with at least one SSC – proportion of subjects in the SOC dressing group with at least one SSC.

8.4.2. Sample Size Determination

The primary endpoint of this study is the subject incidence of SSC as defined in section 4.11.1. The incidence rates of SSC are different for septic and aseptic revisions; the assumed SSC rate is 33% for septic and 6.9% for aseptic. This study plans to enroll at least 50% septic revisions overall. These enrollment rates lead to an assumed pooled SSC rate of 20% in the SOC dressing arm.

Assuming an overall type 1 error rate of 0.05, with a two-sided hypothesis test, the study will have at least 80% power to detect a difference of 10% (50% reduction) in SSCs in the ciNPT arm with 199 subjects in each treatment arm, with one interim analysis at about 50% of the evaluable subjects for a total of 398 subjects using the likelihood ratio test. With an estimated 5%-10% loss, a non-binding interim analysis for superiority at approximately 50% of the evaluable subjects using O'Brien-Fleming method for monitoring boundaries, the planned sample size will be inflated for potential loss of follow-up for a total of 440 subjects.

8.4.3. Randomization

Subjects who meet all inclusion criteria and no exclusion criteria will be randomized in a 1:1 ratio to either the ciNPT or SOC dressing treatment arm. The randomization will be stratified by status at revision (septic versus aseptic).

For each stratum, a randomization schedule including randomization numbers and treatment assignments will be generated and maintained centrally in the web-based clinical database management system. Once randomized, a subject's assignment cannot be altered or changed; a subject should not be randomized twice.

8.4.4. Open-Label Study Reporting Results

In order to reduce operational bias that can be introduced during the analysis, while the study is ongoing summary statistics by treatment groups across all sites will be limited to a small analytical group at the Sponsor not involved in the daily operations of the study. Treatment groups will be masked in the summary outputs (tables, listings, and figures) in order to reduce the inference should results be inadvertently accessed. The limited results of the interim analysis will be shared with Investigators and IRBs as necessary to conduct the study.

Upon study completion, the full results will be shared with all investigators and clinical sites.

8.4.5. Interim Analysis

An interim analysis may be conducted at information-time $t=0.5$, i.e., when approximately half the planned study subjects [$n=200$] have had their primary endpoint assessed. The interim analysis will be performed at the $\alpha=0.0052$ level; if the p-value for the primary endpoint is < 0.0052 , the study will be stopped and null hypothesis rejected. Otherwise, the final analysis will be conducted at $\alpha=0.048$ (i.e., by constructing a 95.2% confidence interval) to preserve overall Type I error rate at 5%. These α values were chosen using an O'Brien-Fleming α -spending function assuming $t = 0.5$. The alpha levels that will be used at the interim and final will be calculated according the precise information time at the interim analysis.

If warranted, based on the unblinded interim results, the final sample size may be increased using appropriate statistical methodology as described in Chen.²³ The increase to the final sample size would only occur if the interim results had conditional power of success $\geq 50\%$, would be subject to the restrictions in Chen, and would not be considered statistically binding.

At the interim analysis, the rate of SSC for septic and aseptic revisions will be examined to confirm assumptions of the sample size calculations.²⁴ In addition, the rate of SSC will be independently assessed for septic and aseptic revisions at the interim analysis to determine if a modification of enrollment from a 1:1 ratio of septic:aseptic revisions to focus on enrollment for either revision type is needed. This type of adaptive enrichment design will be further detailed in the interim statistical analysis plan.²⁵

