6 INTERIM ANALYSIS

As stated in the protocol, an interim analysis will be conducted at information-time $t=0.5$, i.e., when approximately half the planned study subjects have had their primary endpoint assessed. The interim analysis will be performed at the $\alpha=0.0052$ level; if the p-value for the primary endpoint is < 0.0052 , the study will be stopped, and the null hypothesis rejected. Otherwise, the final analysis will be conducted at $\alpha=0.048$ (i.e., by constructing a 95.2% confidence interval) to preserve overall Type I error rate at 5%. These α values were chosen using an O'Brien-Fleming α -spending function assuming $t = 0.5$. The alpha levels that will be used at the interim and final will be calculated according to the precise information time at the interim analysis.

If warranted, based on the unblinded interim results, the final sample size may be increased using the appropriate statistical methodology as described in Chen et al. [2004]². Per Section 8.4.5 of the study protocol, it stated the increase to the final sample size would only occur if the interim results had a conditional power of success $\geq 50\%$, would be subject to the restrictions in Chen et al. [2004]², and

would not be considered statistically binding. However, the interim SAP further clarified that an increase to the final sample size could occur if the conditional power is below 50%. If the sample size is increased when conditional power is $\geq 50\%$, a type I error rate would not be inflated as mentioned in Chen et al. [2004]². If the sample size is increased when conditional power is $< 50\%$, an adjustment will be needed to control the Type I error. The adjustment was outlined in Section 7.3 of the interim SAP.

At the interim analysis, the rate of SSC for septic and aseptic revisions will be examined to confirm assumptions of the sample size calculations. In addition, the rate of SSC will be independently assessed for septic and aseptic revisions at the interim analysis to determine if a modification of enrollment from a 1:1 ratio of septic or aseptic revisions to focus on enrollment for either revision type is needed.

In the final analysis, the type I error rate ($\alpha=0.048$) for statistical significance will be used for the primary and secondary analyses using the O'Brien-Fleming method per study protocol.

Both, the interim SAP and the interim analysis results, will be included in the final clinical study report for this study.

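### The interim and final levels 0.0052 and 0.048 are the classical O'Brien-Fleming boundary, not the alpha-spending function the plan names, so the recalculation it orders would change the stopping level even at t = 0.5

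*Protocol*

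**What the plan says.** Protocol 8.4.5 plans one look at information time 0.5, when "approximately half the planned study subjects [$n=200$] have had their primary endpoint assessed". The stopping rule is definite: "if the p-value for the primary endpoint is < 0.0052 , the study will be stopped and null hypothesis rejected". Otherwise the final test uses 0.048. SAP section 6 repeats both levels and links the final one to error control: "by constructing a 95.2% confidence interval) to preserve overall Type I error rate at 5" percent.

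Both sections give the origin of the two numbers as an O'Brien-Fleming alpha "spending function assuming" t = 0.5. Both then add a recalculation rule; in the protocol's words, "The alpha levels that will be used at the interim and final will be calculated according the precise information time" at the interim.

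Other sections bear on this:

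- Protocol 8.4.2 and SAP 2.1 refer only to an O'Brien-Fleming method for the monitoring boundaries and mention no spending function.
- Protocol 8.3.4 gives 0.048 as an example, conditional on a look at t = 0.50 and no sample size change.
- SAP 6 (closing paragraphs) and SAP 8.5 fix the final level at 0.048 without that condition.
- Neither document writes out a spending function.

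**The concern.** The classical O'Brien-Fleming boundary and the O'Brien-Fleming-type spending function are related but give different numbers at two looks. The printed numbers belong to the first and the stated method is the second.

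That would be only a naming slip if the printed numbers were final. They are not, because the same paragraph tells the analyst to recompute them at the achieved information time. An analyst who does so with the named function will not get 0.0052 back, even if the look falls at exactly t = 0.5. The plan therefore supports more than one interim threshold for stopping the trial and rejecting the null. The final level has a related conflict: it is to be recalculated in one paragraph and is fixed at 0.048 in others.

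**Working it through.** **Inputs.** Overall error comes from Protocol 8.4.2: "Assuming an overall type 1 error rate of 0.05, with a two-sided hypothesis test". There are two looks, the first at t = 0.5 (Protocol 8.4.5). Planning rates are 20% and 10% with 199 evaluable per arm (Protocol 8.4.2).

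**Method.** The two test statistics are treated as bivariate normal with correlation √t. Each boundary pair (z1, z2) is solved so that P(|Z1| ≥ z1 or |Z2| ≥ z2) = 0.05 under the null. Nominal levels are 2(1 − Φ(z)).

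**1. Reproducing the printed pair.** The classical boundary sets z1 = C/√t and z2 = C. At t = 0.5, C = 1.9774 and z1 = 1.9774/0.7071 = 2.7965. The levels are 0.00517 and 0.04799, which round to the printed 0.0052 and 0.048.

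**2. The named method.** The documents give no formula, so both usual readings of the O'Brien-Fleming-type (Lan-DeMets) function are shown at t = 0.5.

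- *0.025 per side:* the spend per side is 2 − 2Φ(2.2414/√0.5) = 2 − 2Φ(3.170) = 0.001525. Doubling gives 0.00305, so z1 = 2.963. Solving for the second look gives z2 = 1.969, level 0.0490.
- *Two-sided 0.05 entered directly:* 2 − 2Φ(1.960/√0.5) = 2 − 2Φ(2.772) = 0.00557. The final level is 0.0478.

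Neither gives 0.0052. The 0.025-per-side form reaches 0.0052 only at t = 0.554, with a final level of 0.0483. Two other spending families also miss at t = 0.5: the power family with rho = 3 gives 0.00625/0.0474, and Hwang-Shih-DeCani with gamma = −4 gives 0.0060/0.0476.

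**3. Overall two-sided error at t = 0.5.**

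| Interim | Final | Overall error |
|---|---|---|
| 0.0052 | 0.048 (as printed) | 0.0500 |
| 0.00305 | 0.0490 | 0.0500 |
| 0.00305 | 0.048 | 0.0490 |
| 0.0052 | 0.049 | 0.0510 |

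**4. Effect on early stopping.** At the interim there are 199/2 = 99.5 per arm. The expected Z is 0.10/√(v/99.5), where v = 0.20×0.80 + 0.10×0.90 = 0.25 (unpooled) or 2×0.15×0.85 = 0.255 (pooled), giving 1.995 or 1.975. The chance of stopping is 1 − Φ(z1 − expected Z).

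| Interim level | z1 | Chance of stopping (pooled to unpooled) |
|---|---|---|
| 0.0052 (printed) | 2.794 | 20.6% to 21.2% |
| 0.00305 | 2.963 | 16.2% to 16.7% |
| 0.00557 | 2.772 | 21.3% to 21.9% |

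The band in which the printed level and the named method disagree therefore has probability of about 21.2 − 16.7 = 4.5% under the 0.025-per-side form. Under the direct form it is about 21.9 − 21.2 = 0.7% unpooled; before rounding, both variances give about 0.65%.

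**5. Power and sample size.** Two-look power at 199 per arm is 0.795 to 0.802 with the classical pair and 0.796 to 0.804 with 0.0031/0.0490. The 0.0056/0.0478 pair gives about 0.80 as well. The sample size is unaffected.

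**The case against.** The strongest reply is that the printed pair works. It holds overall error at 0.050, and 0.048 is the final level wherever the plan states one. The sample size sections, and the closing paragraphs of SAP 6, speak of the O'Brien-Fleming method, which fits the classical boundary. On that view one sentence, repeated in two documents, uses a loose term. This largely stands, and a reader who infers type I error inflation from the mismatch would be wrong. Inflation needs the two schemes to be mixed. The worst such pairing considered here, 0.0052 followed by 0.049, gives 0.051, and neither document prints 0.049.

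A second reply is that the 0.0031 figure assumes a formula the plan does not give. This also stands. With two-sided 0.05 entered directly the interim level is 0.0056, the printed level becomes the stricter one, and the disputed band shrinks to about 0.65%. But 0.0052 is not reproduced either way.

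A reader might also infer that the threshold could be picked once the interim p-value is known. The documents do not support that. Protocol 8.4.5 ties the levels to information time, and Protocol 8.4.7 requires the interim SAP to be final before the interim analysis. That interim SAP is not among the documents and may settle the function.

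Finally, a reader might divide 200 by 440 and take t as 0.4545, which would widen the gap. Protocol 8.4.2 places the look at about half of the evaluable subjects, who number 398, so t = 200/398 = 0.5025. There the classical pair is 0.0053/0.0480 and the 0.025-per-side pair is 0.0031/0.0490, almost the same as at 0.5.

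What the replies do not remove is the recalculation rule. It makes the named method operative, and the named method does not return the printed level.

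**Conclusion.** The concern holds as an inconsistency between method and numbers, not as a failure of error control. The levels 0.0052/0.048 are the classical boundary, while the plan attributes them to a spending function that gives 0.0031/0.0490 or 0.0056/0.0478 at the same t. Because recalculation is ordered, the interim stopping level is not uniquely defined by these two documents.

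The practical size is modest: about a 4.5% chance under the planning rates that the interim p-value falls where the two rules disagree, or about 0.65% under the other form. Power stays near 80%. These figures rest on the normal approximation, the planning rates of 20% and 10%, and the standard O'Brien-Fleming-type spending function. The arithmetic is certain, but the effect on an actual decision is less so, since the interim SAP may specify the rule. It should be corrected because it concerns a decision threshold and costs almost nothing to fix.

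**What to change.** Before the interim analysis, make the name and the numbers agree in Protocol 8.3.4 and 8.4.5 and SAP 6 and 8.5. Either:

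- name the classical O'Brien-Fleming boundary, keep 0.0052/0.048 at t = 0.5, and state that the constant C is recomputed at the actual t; or
- keep the spending function, write its formula, and print the matching pair: 0.0031/0.0490 with a 95.1% interval, or 0.0056/0.0478 with a 95.2% interval.

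In either case, replace the fixed final 0.048 in SAP 6 and 8.5 with the level recalculated at the actual information time, giving 0.048 only as the illustrative value where it applies. Confirm that the interim SAP uses the same rule.

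The cost is a sentence and at most two numbers in each place, with no change to sample size. The one downside is that under the 0.025-per-side form early stopping becomes slightly harder (about 16-17% instead of about 21% at the planning rates), in exchange for a slightly larger final level.

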8.4.6. Study Sites

This is a multi-center study following the same protocol and procedures. It is anticipated that approximately 15 study sites in North America will participate, and each site will randomize and treat subjects in both treatment groups. The data and the results of the study will be pooled across clinical sites and centers.

8.4.7. Statistical Analysis Plans and Changes in Analyses

Statistical Analysis Plans (SAPs) containing full details of the statistical analyses and execution will be prepared for both the interim analysis and the final analysis. The interim SAP (iSAP) will be finalized prior to conducting interim analysis. The final SAP (fSAP) will be finalized prior to locking the study database and the final analysis. Any changes from the planned analyses in this protocol, the iSAP, and/or the fSAP will be noted in the Clinical Study Report (CSR).

9. HANDLING OF STUDY PRODUCTS

Study product receipt, use, dispensation, destruction, and return records will be maintained throughout the study.

Upon receipt of product, the Investigator, or designee, will inventory the shipment and immediately notify KCI if study product or other study supplies are missing. The KCI monitor will verify that study product documentation is maintained appropriately during monitoring visits.

At the completion of the study, there will be a final reconciliation of study product shipped, used, and unused. Any unused study product and associated supplies will be returned to KCI.

10. DATA HANDLING AND RECORD KEEPING

10.1. Investigator/Study Site Training

The Investigator and site staff will be trained on the protocol, the study products, and any specialized procedures prior to enrolling subjects into the study. KCI will provide support to site staff for any questions or concerns related to study products and procedures. KCI will not have influence on subject medical care.

10.2. Electronic Case Report Form (eCRF) and Source Documents

Source documents include all information in original records, certified copies of original records, observations, or other activities necessary for the reconstruction and evaluation of the study. All source documents should be completed in their entirety in a neat, legible manner to ensure accurate interpretation of the data.

Data from source documents of each subject will be entered into the subject's electronic Case Report Form (eCRF). Guidance for eCRF completion will be provided and reviewed with the site staff prior to receiving study product.

10.3. Monitoring of Study Data

The Investigator will allow access to his/her clinical study records for periodic on-site monitoring visits by a designated KCI representative, with the understanding that the representative is bound by professional secrecy and will not disclose a subject's personal identity or personal medical information. The representative will review eCRFs for completeness during on-site monitoring visits and after the eCRFs are submitted; any discrepancies will be resolved with the Investigator or designee, as appropriate. The data will be entered into the clinical study database and verified for accuracy.

10.4. Data Handling

KCI is responsible for compilation and verification of the clinical study data, retention of the clinical study database, performance of statistical analysis, and preparation of the clinical study report.

10.5. Records Retention

The study site will maintain all study documentation and institute measures to prevent accidental or premature destruction of any data and/or documents related to the study.

After formal discontinuation or completion of the study, the Investigator will retain all clinical study documentation for a minimum of two (2) years from the date the investigation is terminated or completed or in accordance with the regulations in effect for the

jurisdiction where the site is located. The Investigator will contact KCI prior to the destruction of any study records.

11. ADMINISTRATIVE REQUIREMENTS

11.1. Good Clinical Practice (GCP)

This study is to be conducted according to US and international standards of good clinical practice (FDA Title 21 part 812 and International Conference on Harmonization guidelines), applicable government regulations and institutional research policies and procedures.

11.2. Ethical Considerations

This study will be conducted in accordance with ethical principles founded in the Declaration of Helsinki. Approving IRBs will be provided all relevant study documentation in order to safeguard the rights, safety, and well-being of subjects as mandated. Participating Investigators will obtain IRB approval of the study prior to initiation at their sites. The protocol, Instructions for use, informed consent, written information given to subjects, safety updates, and any revisions to these documents will be provided to the IRB by the Investigator.

11.3. Subject Informed Consent

Written informed consent will be obtained from a potential Subject after the study has been fully explained and prior to the conduct of any study-related procedures. Obtaining informed consent is a process that must be documented in compliance with GCP, IRB and other applicable regulatory requirements (21 CFR part 50). The Investigator is responsible for continuing an open conversation with the subject in regard to their continued participation in the study. KCI will conduct periodic monitoring to ensure informed consent is obtained from each Subject prior to any study procedures.

11.4. Confidentiality

Information collected about subjects during the study will be kept confidential and managed according to the requirements of the IRB and Health Insurance Portability and Accountability Act of 1996 (HIPAA).

In the event that a subject revokes authorization to collect or use Personal Health Information (PHI), the Investigator retains the ability to use all information collected prior to the revocation of subject authorization.

11.5. Clinicaltrials.gov Registration

A description of this study will be available on <http://www.ClinicalTrials.gov> as required by U.S. law. This website will not include information that identifies subjects. At most, the website will include a summary of the results of the study and will be available for public review at any time.

11.6. Auditing and Inspecting

Participation as an Investigator in this study implies acceptance of potential inspection by government regulatory authorities and applicable compliance and quality assurance offices.

The Investigator will permit study-related monitoring, audits, and inspections of all study related documents (e.g., source documents, regulatory documents, data collection instruments, study data) by the IRB/IEC, KCI, and government regulatory bodies.

12. PUBLICATION POLICY

The publication policy for this study will be addressed in a separate agreement.

14. APPENDICES

14.1. KOOS Questionnaire

14.2. PROMIS 10 Questionnaire

1 PURPOSE

The purpose of this Statistical Analysis Plan (SAP) for the KCI.PREVENA.2017.01 study is to outline the analyses planned to support the generation and completion of the Clinical Study Report (CSR). This SAP has been written to be in accordance with the clinical protocol (**Post-market, Randomized, Open-Label, Multicenter, Study to Evaluate the Effectiveness of Closed Incision Negative Pressure Therapy versus Standard of Care Dressings in Reducing Surgical Site Complications in Subjects with Revision of a Failed Total Knee Arthroplasty Version 3.0 dated October 6th, 2018**) and relevant data collection documents. This SAP adheres to the requirements and guidelines identified by the U.S. Food and Drug Administration (FDA), European Medicines Agency (EMA), International Conference on Harmonization (ICH) of Technical Requirements for Registration of Pharmaceuticals for Human Use: Guidance on Statistical Principles in Clinical Trials [1998]¹.

The planned analyses identified in this SAP may be included in clinical study reports (CSRs), regulatory submissions, or future manuscripts. Post-hoc exploratory analyses not identified in this SAP may be performed to examine study data further. Any post-hoc or unplanned exploratory analysis will be identified as such. This document will be endorsed prior to database lock. Changes made to the SAP prior to the final database lock will be described in the document history. The SAP will not be amended after the final database lock. Deviations from planned analyses, including additional exploratory analyses after database lock will be noted in the CSR.

